3.3. RATIONALE FOR THE STUDY

The aim of this observational study is to collect individual data from patients with CIBP to better characterize the source of pain and patient's specificities in terms of primary disease history and personality traits to improve analgesic treatment recommendation.

4. STUDY DESIGN

4.1. DESCRIPTION OF STUDY DESIGN

This multicentre study is an observational study collecting data in cancer patients with bone metastasis suffering from pain.

This study will include up to 180 patients with bone tumor or metastasis from any primary cancer origin that are supported by histological or radiological investigations corresponding to CIBP.

Patients will be treated by the Investigators for pain relief exactly as they would normally be based on their needs and clinician practice. The enrolled patients must be requiring analgesic treatment. They will be followed over a period from 4 to 10 weeks. The analgesic treatment will be reviewed based upon patient's needs and patient general health status collected throughout the entire study.

During the study, visits may be adapted according to Investigator-patients agreement, as presented in Section 8.5.4. Patients may also visit the Investigator as many times as required by their pain conditions.

Depending on patients/Investigator site availabilities, Visit 1 assessments may be performed in one visit (Visit 1) or 2 visits (Visit 1A and Visit 1B).

The design of the study for the 2 case scenarii is illustrated in Figure 1.

[figure not shown]

Figure 1¹. Study Design when Visit 1 Assessments are Performed at the Same Visit/ Screening and Enrolment at Visit 1

[figure not shown]

Figure 1". Study Design when Visit 1 Assessments are Performed in 2 Visits – Screening and Enrolment at Visit 1A

Figure 1. Study Diagram

4.1.1. SCREENING AND ENROLMENT VISIT

FIRST CASE SCENARIO: SCREENING AND ENROLMENT AT VISIT 1

In this case scenario, all Visit 1 assessments are performed during only one visit, this visit will take place as described below.

First, the study purpose – including the optional genotyping research study - will be explained to patients who will then sign and date the Informed Consent Document (ICD) before completing any study procedure. In addition, patients who consent to take part in the genotyping exploratory research will also sign a specific genotyping ICD to allow the use of their archived tumor tissue block, if any and/or of an aliquot of standard safety laboratory blood sample.

Patients' WAPS will be collected and a value of at least 4 will be required to take part in the study. Patients' standard demographic, relevant medical and primary disease history, primary disease treatment history, analgesic treatment history up to one month prior to entry into the study, symptoms related to analgesic treatment, if any as well as cancer concomitant therapies will then be recorded. Patients will also undergo an abbreviated physical examination.

[figure not shown]
After checking completion of all inclusion/exclusion criteria, eligible patients will be enrolled in the study and perform the baseline Clinical Pain Assessments (CPAs). The following questionnaires will also be completed: pain disease questionnaires (DN4, NPSI and PCS), Brief Pain Inventory (BPI) questionnaire, expectation questionnaire, personality traits questionnaires (MHLCS, HADS and LOT-R) and quality of life questionnaire (Quality-of-Life Questionnaire in 30 questions (QLQ-C30)). The PGAC and IGAC will be completed by the patient and the Investigator, respectively.

At the end of the Visit and after patient evaluation, the Investigator will initiate or review as necessary the analgesic treatment and the patients will enter an observational period of approximately 4 weeks.

Before patients leave the site, Investigator site staff will dispense them a diary and educate them on proper completion of the 2 pain scales, the daily APS and WPS. The APS measures the average pain intensity over the last 24 hours; the WPS, the worst pain intensity over the last 24 hours, both on an 11-point Numeric Rating Scale (NRS) where 0 means no pain and 10, pain as bad as you can imagine. The APS and WPS of Visit 1 day will be completed by the patients at site with investigator site staff help. Between Visit 1 and Visit 2, the patients will also be asked to report in their diary intake of additional to prescribed analgesic treatment (rescue analgesic treatment), if any.

For a complete list of assessment procedures to be performed at Visit 1, see Study Schedule – Enrolment at Visit 1 - Section 16.1. Study Visit 1 is also depicted in Figure 2.

Patients will spend about 3 hours at the Investigator site during this visit.

Abbreviations: BPI = Brief Pain Inventory; DN4= Douleur Neuropathique en 4 questions; HADS = Hospital Anxiety and Depression Scale; ICD= Informed Consent Document; ICD DNA= Informed Consent Document for genotyping research; IGAC=Investigator Global Assessment of Changes; LOT-R = Revised Life Orientation Test; MHLCS = Multidimensional Health Locus of Control Scale; NPSI= Neuropathic Pain Symptom Inventory; PCS= Pain Catastrophizing Scale; PGAC= Patient Global Assessment of Changes; QLQ-C30=quality-of-life questionnaire in 30 questions; WAPS: Weekly Average Pain Score

Figure 2. Sequence of Assessments at Visit 1

SECOND CASE SCENARIO: VISIT 1 ASSESSMENTS PERFORMED IN 2 VISITS – SCREENING AND ENROLMENT AT VISIT 1A

In this case scenario, Visit 1A and Visit 1B will be organized as follows. Eligible patients will be enrolled into the study at Visit 1A (screening and enrolment visit) but a few defined questionnaires will be completed at Visit 1B one to four weeks after Visit 1A. For a complete list of assessment procedures to be performed at Visit 1A and Visit 1B, see Study Schedule – Enrolment at Visit 1A - Section 16.2.

Visit 1A: Screening and Enrolment

[figure not shown]
The assessments will be performed as described for Visit 1 in the first case scenario up to patient enrolment into the study. After checking WAPS and completion of all inclusion/exclusion criteria, eligible patients will be enrolled in the study and perform the CPAs. The following questionnaires will be completed during this visit: DN4, NPSI, BPI, Expectation and QLQ-C30. The PGAC and IGAC will be completed by the patient and the Investigator, respectively.

At the end of the Visit and after patient evaluation, the Investigator will initiate or review the analgesic treatment and the patients will enter an observational period of 5 to 10 weeks depending on when Visit 1B is scheduled.

Before patients leave the site, Investigator site staff will dispense them a diary and educate them on proper completion of the 2 pain scales, the daily APS and WPS. The APS and WPS of Visit 1A day will be completed by the patients at site with Investigator site staff help. Between Visit 1A and Visit 2, the patients will also be asked to report in their diary intake of supplemental analgesic treatment (rescue analgesic treatment), if any.

Study Visit 1A is depicted in Figure 3.

During this visit, patients will spend about 2 hours at Investigator site.

Abbreviations: BPI = Brief Pain Inventory; DN4= Douleur Neuropathique en 4 questions; ICD= Informed Consent Document; ICD DNA= Informed Consent Document for genotyping research; IGAC=Investigator Global Assessment of Changes; NPSI= Neuropathic Pain Symptom Inventory; PGAC= Patient Global Assessment of Changes; QLQ-C30=quality-of-life questionnaire in 30 questions; WAPS: Weekly Average Pain Score

Figure 3. Sequence of Assessments at Visit 1A

Visit 1B

This visit will start with checking compliance to prescribed analgesic treatment and diary completion instructions. MHLCS, HADS, LOT-R questionnaires and PCS questionnaire will then be completed by the patients. The Investigator will review the analgesic treatment.

4.1.2. OBSERVATIONAL PERIOD – INTERMEDIATE PHONE CALL

The observational period is a 4- to 10-week analgesic treatment therapy period including a phone call scheduled approximately 2 weeks after Visit 1 or Visit 1B (See figure 1. Study Diagram).

During this phone call, the Investigator site staff will inquire about patient general health status and pain relief. The patient will be reminded about Visit 2 scheduled date, diary and prescribed analgesic treatment compliance. At the end of the phone call, an intermediate visit to Investigator site may be organized within the next days at the discretion of Investigator.

If organized, this visit will start with collection of the diary, checking compliance to diary completion instructions and to prescribed analgesic treatment. Patient will complete BPI and go through all CPAs. At the end of this optional visit, the Investigator will review the analgesic treatment. Patients will continue to complete a diary up to Visit 2.

For a complete list of assessments to be performed at Intermediate Evaluation Visit, see Study Schedule Sections 16.1. and 16.2. This optional visit is also depicted in Figure 4.

At this visit, patients will remain at the Investigator site for approximately 1 hour.

[figure not shown]

[figure not shown]
Figure 4. Sequence of Assessments at Intermediate Evaluation Visit

4.1.3. VISIT 2: END OF OBSERVATIONAL PERIOD AND FOLLOW-UP VISIT

Approximately 4 weeks after Visit 1 or Visit 1B (depending on the case scenario selected to complete Visit 1 assessments), Visit 2 will start with collecting the diary, checking compliance to diary completion instructions. All patients will complete BPI, PGAC and QLQ-30, while Investigator will complete IGAC as described in Figure 5. In addition, patients will undergo an abbreviated physical examination and the last CPAs. At the end of Visit 2, the Investigator will review patients analgesic treatment therapy.

For a complete list of assessments to be performed at Visit 2, see Study Schedule Sections 16.1. and 16.2.

Patients will remain at the Investigator site for approximately 1 hour at Visit 2.

Abbreviations: BPI = Brief pain Inventory; IGAC = Investigator Global Assessment of Changes ; PGAC= Patient Global Assessment of Changes; QLQ-C30 = Quality-of-Life Questionnaire in 30 questions.

Figure 5. Sequence of Assessments at Visit 2

Phone Call: End of Data Collection

A phone call will take place approximately 1 week after Visit 2. Patients will provide their last APS and WPS and give information on their current analgesic treatment. This phone call will last less than 10 minutes.

4.2. RATIONALE FOR THE STUDY DESIGN

4.2.1. POPULATION SELECTION AND SAMPLE SIZE

It is intended that up to 180 patients with CIBP will be enrolled to ensure that up to approximately 140 patients complete the study.

No a priori hypothesis tests or precision confidence intervals were used to determine the sample size. This sample size is rather justified by similar studies described in literature.

In the field of CIBP, several works have been reported. For example, Langford studied 97 cancer patients with CIBP, and managed to model the pain evolution for a particular subgroup of patients (Langford et al. 2011). Scott showed a link between QST and analgesia response on 23 patients suffering from CIBP. In other domains that are close, other works have been reported as well (Scott et al. 2012). First, Attal managed to show the relation between a pain-related marker (thermal hyperalgesia) and oxalyplatin neurotoxicity in cancer patients, based on a cohort of 48 patients (Attal et al. 2009). Second, Geber showed the ability of some psychological traits to discriminate between patient subgroups with different pain evolution scenarios based on a cohort of 146 patients suffering from chemotherapy-induced neuropathy (Geber et al. 2013).

The considered sample size for this trial seems therefore reasonable: higher than the sizes of the samples cited above. This larger number is motivated by the more complete set of features studied in the current study (patient history, psychological traits, pain assessments). Moreover as presented in Section 4.2.3, an interim analysis will be performed to confirm the final sample size of the study.

4.2.2. JUSTIFICATION FOR STUDY DESIGN

This study is an observational study. This design has been selected to collect data of analgesic treatment that would reduce pain severity after 4 to 10 weeks of analgesic treatment administration to patients.

4.2.3. INTERIM ANALYSIS

An interim analysis is planned after study completion of approximately 60 patients. Its main objective is to confirm the considered sample size of approximately 140 patients completing this study. Its secondary objectives will be to confirm questionnaires and historical data to be collected.

At this stage, each input feature (e.g. questionnaire items, historical data) will be evaluated with respect to its ability to discriminate on its own (i.e. not yet in conjunction within a set of features) between several levels of pain evolution. In case a non-significant correlation is found for a feature, the estimated sample size required will be computed. This analysis will allow getting a view on which features might show satisfactory results with a number of patients below 140.

The outcome of the interim analysis can therefore be either a confirmation of the initial sample size or a decrease of the number of required patients if striking relations are observed between a sufficiently high number of patients' features and pain-related outcomes (as defined by primary and/or secondary endpoints).

If following the interim analysis, substantial changes were to be brought to study, protocol and ICD would be amended and submitted for approval.

5. POPULATION RECRUITMENT, ENROLMENT AND WITHDRAWAL

5.1. DEFINITIONS

Screening Failure:

A patient is considered as a screening failure when he/she is screened but not enrolled in the study as not meeting eligibility criteria.

Patient Enrolment:

A patient is considered as enrolled in the study when he/she meets all eligibility criteria and he/she performs CPAs at Visit 1 or Visit 1A.

Patient Dropout:

A patient will be considered as dropout when, for any reason, he/she withdraws from the study or is discontinued from the study prior to study completion.

5.2. POPULATION RECRUITMENT

Patients will be recruited on a free voluntary basis. The criteria for enrolment must be followed explicitly. The Investigator(s) should demonstrate due diligence in recruitment and screening of potential study patients.

As illustrated in Sections 16.1 and 16.2 Study Schedule, eligibility of patients in the study will be based on the results of a screening visit.

5.3. INCLUSION DISEASE CRITERIA

Patients are eligible to be included into the study if they meet all of the following CIBP disease diagnosis criteria:

- [1] Patients with bone tumors or bone metastasis from any primary cancer origin that is supported by histological or radiological investigations.
- [2] Patients having been or being treated for their bone metastasis and/or their primary cancer.
- [3] Patients who require analgesic treatment for unsatisfactory pain relief.
- [4] Patients will be required to score at least 4 on the WAPS 11-point NRS during the week preceeding enrolment.
- [5] Patients undergoing or not a radiotherapy program provided visit procedures are performed before any radiotherapy sessions if scheduled on the same visit days.

5.4. INCLUSION CRITERIA

Patients may be included in the study only if they meet all of the following criteria:

- [6] Are men or women of at least 18 years of age.
- [7] Being affiliated to country welfare.

- [8] Are reliable and willing to make themselves available for the entire duration of the study and are willing to follow study procedures.
- [9] Have given written informed consent approved by the relevant Ethics Committee (EC) governing the study site.

5.5. EXCLUSION DISEASE CRITERIA

Patients will be excluded from the study if they meet any of the following criteria related to CIBP:

- [1] Patients having had a major surgery within 28 days prior to signing ICD or planning to have a major surgery during the study.
- [2] Patients having a life expectancy < 3 months according to Investigator judgment.

5.6. EXCLUSION CRITERIA

Potential study patients may not be entered into the study if they meet any of the following criteria:

- [3] Patients having poor nutritional status or whose condition is unstable or who could be rapidly deteriorating in such a way that they would not be able to complete the study.
- [4] Patients with a current or recent history unrelated to their cancer condition, as determined by the Investigator, of severe, progressive, and/or uncontrolled renal, hepatic, hematological, gastrointestinal, endocrine, pulmonary, cardiac, neurological, or cerebral disease which would interfere with the patient's participation in the study.
- [5] Patients having a Karnofsky performance status below 70% or WHO score (Eastern Cooperative Oncology Group (ECOG)/Zubrod score) above 1.
- [6] Are Investigator site staffs directly affiliated with this study and/or their immediate families. Immediate family is defined as a spouse, parent, child, or sibling, whether biological or legally adopted.
- [7] Any other relevant medical disorder likely to interfere with the trial or represent a risk for the patient.
- [8] Patients under legal protection, according to the country law.
- [9] Patients currently enrolled in a clinical trial involving use of an investigational drug or device, or concurrently enrolled in any other type of medical research judged not to be scientifically or medically compatible with this study, or in an exclusion period according to the national law.

5.7. RANDOMIZATION

Not applicable.

5.8. PATIENT WITHDRAWAL, DISCONTINUATION AND REPLACEMENT

5.8.1. WITHDRAWAL /DISCONTINUATION CRITERIA

All patients are free to withdraw their consent to participate in the study at any time, for any reason, specified or non-specified, and without penalty.

The Sponsor and/or the Investigator for some possible reasons listed below may discontinue a patient from the study:

- If, in the opinion of the Investigator and/or the Sponsor, patient's general health status contra-indicates patient continuation in the study,
- The Investigator or delegate decides that the study participant should be withdrawn from the study,
- Non-compliance of the patient with study instructions, such as the patient fails to return to the study site for a scheduled visit and/or does not respond to the attempts of the study site staff to contact him/her (considered as lost to follow-up).

All cases of discontinuation will be discussed between the Investigator and the Sponsor.

5.8.2. FOLLOW-UP PROCEDURES FOR DROP-OUT PATIENTS

In case a patient enrolled in the study drops out or is discontinued from the study earlier than study end, he/she will answer a few questions by phone as indicated in the early discontinuation phone call described in Sections 16.1 and 16.2 Study Schedule. The reason and date for dropout should be documented.

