2.2. PRIMARY ENDPOINT

Individual analgesic treatment efficacy endpoint: patient's change from baseline of pain severity, as measured by the weekly means of the daily Average Pain Scores (APS).

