7.2.2.1. Diary

Once a day from enrolment till Visit 2, approximately at the same time of the day in the evening, patients will complete their diary.

The following data will be recorded:

- pain intensity assessment by recording APS and WPS for the last 24 hours (from enrolment till Visit 2 or early discontinuation). See Sections 8.2.4.4 and 8.2.4.5 for further description of APS and WPS,
- any potential event that may help to understand unexpected study outcomes,
- intake of rescue analgesic treatment if any (from enrolment to Visit 2 or early discontinuation).

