8.5.5. COMPLIANCE TO DIARY COMPLETION

Compliance to diary completion (APS, WPS, rescue analgesic treatment recording) will be checked by Investigator at each visit at Investigator site.

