10.2. DATA CAPTURE

The following source data may be generated and handled for further data basing process:

- Data captured in electronic CRFs (e-CRFs),
- Paper-based data captured systems (i.e. diary, questionnaires).
- Electronic Data Capture systems (analysis,...)

To ensure accurate, complete, and reliable data, the Sponsor will provide instructional material to the study sites, as appropriate. Training session will be given during a start-up/initiation meeting for instructions on completion/data entry of any source data.

The Investigator or his/her designee must verify that all data entries in the e-CRFs are accurate and correct.

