- ^b Potential historical safety laboratory data (biochemistry, hematology) defined as the most recent safety laboratory data obtained within one month before screening visit and/or standard safety laboratory analysis and urinalysis performed during the study as part of regular patient management by Investigator will be collected (one per week if several during the study).
- ^c Compliance to prescribed analgesic treatment will be followed through diary completion and direct questioning.
- ^d The Clinical pain assessments will include the following measurements: MPA, SA, DMA, MPT and TPS.
- ^e APS and WPS will be collected in the diary. APS and WPS at visit 1A will be completed at site by patient with Investigator site staff help, if needed. The last APS and WPS will be completed by patients during the phone call with the Investigator. At Visit 1A, the Weekly APS during the preceeding week will be assessed for enrolment.
- ^f Optional Intermediate Evaluation Visit will be organized within the next days after the intermediate phone call at the discretion of the Investigator.

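### No protocol step retrieves a dropout's paper diary of daily pain scores, and the SAP's completers-only set would exclude those days even if they came back

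*Protocol*

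**What the plan says.** The primary endpoint (Protocol 2.2; SAP 2.4) is the change from baseline in weekly means of daily APS. The SAP adds the daily APS and its linear slope as a secondary endpoint (SAP 2.5).

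- **Recording.** Footnote e of the schedule in Protocol 16.2 says "APS and WPS will be collected in the diary". Protocol 7.2.2.1 sets the span of the daily scores: "from enrolment till Visit 2 or early discontinuation". Protocol 10.2 lists the diary among the paper sources.
- **Collection.** Two points are stated, both at the site. For the optional intermediate visit: "If organized, this visit will start with collection of the diary" (4.1.2). For the end of observation: "Visit 2 will start with collecting the diary" (4.1.3). At Visit 1B diary completion is checked, but collection is not mentioned (4.1.1). Diary compliance "will be checked by Investigator at each visit at Investigator site" (8.5.5).
- **Dropouts.** On early discontinuation "he/she will answer a few questions by phone as indicated in the early discontinuation phone call" (5.8.2). If the sponsor stops the study, 5.11 allows scheduled procedures, the procedures of that call, or both.
- **Analysis sets.** Protocol 10.1.1 applies the pharmacodynamic analyses to all enrolled patients. The SAP introduction and SAP Section 4 restrict the set to patients who completed, with dropouts excluded.

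**The concern.** The protocol asks a patient to keep daily scores until the day of leaving, but describes no route by which the paper reaches the site after a dropout. A patient who leaves on Day 20 without having had the optional visit holds 20 days of APS, WPS and rescue entries at home.

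A single 24-hour score taken by phone cannot supply a weekly mean, a per-patient slope (A2.1), or a contrast between days with and without a treatment (A3). At stake is whether the all-enrolled analysis in Protocol 10.1.1 can be carried out for dropouts, and whether any sensitivity analysis for dropout could be built later. An analysis set can be revised after the fact; a diary left at home may not be recoverable.

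**Working it through.** The plan states no figure to reproduce here. Protocol 4.2.1 says that the sample size rests on no hypothesis test or precision target. The check is a cross-reading, followed by arithmetic for scale.

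**1. What the early discontinuation call collects.** In the 16.2 schedule, the follow-up / early discontinuation column is marked for symptoms, cancer concomitant medications, and APS and WPS. The diary-compliance row is not marked there. Footnote e describes the scores taken at the call as the last ones. I put no weight on the blank diary-completion row, which may have lost a graphic. Most of the 16.1 grid was not legible in the copy I used, so this step rests on 16.2.

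**2. Whether another route exists.** I found no mail return, retrieval visit or phone transcription in 4.1, 5.8.2, 5.11, 7.2.2.1, 8.5.5, 10.2 or 10.3.

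**3. How many patients.** Up to 180 enrolled and up to about 140 completers (4.2.1): 180 − 140 = 40, and 40/180 = 22.2%. There is no replacement (5.8.3).

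**4. How many days could be affected per patient.**
- First scenario (Table 1): Visit 2 falls on Day 29 to 43; the optional visit on Day 13 to 19.
- Second scenario (Table 2): Visit 2 falls on Day 8 + 28 = 36 to Day 29 + 42 = 71; the optional visit on Day 8 + 12 = 20 to Day 29 + 18 = 47.

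Without the optional visit, up to about 6 weeks (first scenario) or 10 weeks (second) of daily scores have no stated retrieval. With it, only the days after that visit are affected.

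**5. Illustrations under assumptions that the documents do not give.**
- *Days.* Assume 40 dropouts, leaving evenly over 28 days (mean 14), complete diaries and no optional visit. Then 40 × 14 = 560 diary days have no route in. Completers contribute 140 × 28 = 3,920. The share is 560 / (560 + 3,920) = 560 / 4,480 = 12.5%. This is close to a worst case for a 28-day follow-up.
- *Precision of one phone score.* Under first-order autocorrelation of 0, 0.3 or 0.6, a 7-day mean has 0.38, 0.49 or 0.65 of the single-day standard deviation. One score is therefore about 1/0.65 = 1.5 to 1/0.38 = 2.6 times as variable. No planned analysis substitutes one for the other; the ratio only shows why the call does not replace the diary.
- *Effect of a completers-only mean.* If mean APS change differs between dropouts and completers by d, the completers' mean differs from the all-enrolled mean by (40/180) × d: 0.11 points for d = 0.5, and 0.44 points for d = 2.

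**The case against.** The strongest reply is that the SAP analyses completers only and names no dropout analysis in A1 to A3. Every diary could come back and no SAP result would change. This stands. Under the current SAP, any selection effect comes from the analysis set and not from the missing envelope. It does not remove the point, because Protocol 10.1.1 says all enrolled patients and the two documents must be reconciled. A3 in particular needs no Visit 2: it uses patients with some days on and some days off a treatment, so partial diaries could contribute.

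A second reply is that silence is not prohibition. Section 7.2.2.1 expects diary scores up to discontinuation, 10.4 mentions patient diaries among source records, 10.3 leaves missing-data handling to data management plans that are not part of these documents, and 4.1 lets patients attend as often as their pain requires. This also stands. A reader might infer that dropouts' diaries are definitely lost; the documents support only that no retrieval step is specified.

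A reader might also infer that patients with worsening pain lose their curves most often, which would tilt the results towards stable patients. The documents do not show this. Deteriorating health is a listed reason for discontinuation (5.8.1), so informative loss is plausible. Against that, the intermediate call asks about pain relief and may lead to the optional visit, where the diary is collected. Patients with poor relief who are still in the study then may be more likely to have partial diaries on file.

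Finally, 40 is the difference between two upper limits and not a stated dropout rate, and patients who cannot be reached (5.8.1) may return nothing under any procedure.

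**Conclusion.** The point holds as a gap in the specified procedures together with a conflict between the protocol and the SAP. Followed as written, the protocol does not secure the daily APS series of a dropout, although 7.2.2.1 asks for it and 10.1.1 relies on it. Up to about 40 of 180 patients (22%) could be affected, for all diary days or for those since the optional visit. The SAP's completers-only set contradicts 10.1.1 and would exclude these days in any case, so both parts need correction for either to matter.

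The count of 40 assumes enrolment and completion at their stated upper limits. The 560 days, the 1.5 to 2.6 ratio and the 0.11 to 0.44 points are illustrations only. The documents establish neither the size nor the direction of a bias.

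**What to change.** **Protocol (5.8.2, 5.11 and both schedules).** Add to the early discontinuation call that the patient returns the diary in a prepaid envelope or, if it is not returned, reads the daily APS, WPS and rescue entries to site staff. Record the date of the last diary day. Apply the same to ongoing patients if the study is stopped early.

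**SAP (introduction, Section 4, A2.1, A2.3, A3).** Reconcile the analysis set with Protocol 10.1.1. Include every enrolled patient with a prespecified minimum number of diary days, for example 7, in A2.1 and A2.3, and in A3 where its scope rule is met. Keep the completers-only analysis as a sensitivity analysis.

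**Cost.** A small amendment to each document, an envelope per patient and a longer call. Some diaries will still be missing after withdrawal of consent or loss to follow-up.

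Short diaries also give imprecise slopes. With independent daily errors, the slope's standard deviation is proportional to 1/√[n(n² − 1)/12]. The bracket is 7 × 48/12 = 28 for 7 days and 28 × 783/12 = 1,827 for 28 days, so the 7-day slope is √(1,827/28) = 8.1 times as variable. The minimum should be chosen with this in mind, or A2.3 should give less weight to short series.
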